#### **6.9** Protocol Deviations

Information on protocol deviations are to be obtained from the eCRF (*Protocol Deviations* eCRF panel).

Protocol deviations are to be summarized by classification (major or minor) presenting the number of deviations and the number of subjects having the particular deviation. Protocol deviations are to be summarized for the ENR by age group.

All protocol deviations are to be listed for the ENR.

#### 7. EFFICACY EVALUATION

### 7.1 Bleeding Episodes

Results on spontaneous ABR are considered one of the co-primary objectives of this study. All other results related to bleeding episodes form part of the secondary objectives of this study.

The following information is to be obtained from the eCRF:

- Bleeding episodes (*Bleeding Episode* eCRF panels).
- Target joints (Hemophilia A History/ Blood Group/ Family History/ Target Joint Identification and Development of new Target Joints eCRF panels).
- Infusions to treat bleeding episodes and prophylactic infusions prior to bleeds (*Study Infusion* eCRF panels).
- Ultrasound (*Ultrasound* eCRF panel).

The following derivations based on eCRF reported results are to be performed:

- The following anatomical bleeding sites are considered to be joints:
  - o Left wrist.
  - o Right wrist.
  - o Left elbow.
  - o Right elbow.
  - o Left shoulder.
  - o Right shoulder.
  - o Left hip.
  - o Right hip.
  - o Left knee.
  - o Right knee.
  - o Left ankle.
  - o Right ankle.
  - Any free text identified anatomical bleeding site containing the word "Joint". Confirmation from medical is to be obtained on all free text identified joints prior to analysis.
- A joint is considered to be a target joint if:
  - The joint is identified as a target joint from either of the Hemophilia A
     History/ Blood Group/ Family History/ Target Joint Identification and
     Development of new Target Joints eCRF panels.

- There was at least three spontaneous bleeds within six months in the particular joint.
- A joint will cease to be considered as a target joint if identified in the eCRF with less than three spontaneous bleeds within a six month period.
- A bleeding site is considered to be a target joint if the specific joint is considered to be a target joint at the time of the bleed.
- A bleeding site is considered to be a non-target joint if the specific bleed is not considered to be a target joint at the time of the bleed. The bleeding site is still to be considered a joint.
- A bleed is considered to be an injury related bleed if the cause is indicated as "Injury"
- A bleed is considered to be a spontaneous bleed if the cause of bleed is identified as "Spontaneous" or "Unknown" in the eCRF.
- A bleed is considered to be a major bleed if the severity is indicated as "Severe" or "Major".
- A bleed is considered to be a moderate bleed if the severity is indicated as "Moderate".
- A bleed is considered to be a minor bleed if the severity is indicated as "Mild" or "Minor".
- A bleed is considered to be a weekday bleed if the bleed occurred on a Monday, Tuesday, Wednesday, Thursday or Friday.
- A bleed is considered to be a weekend bleed if the bleed occurred on a Saturday or Sunday.
- A bleed is considered to be a morning bleed if the bleed occurred between 04:00 and 11:59.
- A bleed is considered to be an afternoon bleed if the bleed occurred between 12:00 to 17:59.
- A bleed is considered to be a night bleed if the bleed occurred between 18:00 and 03:59.
- A bleed is considered to have occurred at an unknown time if the time of a bleed is not available.
- Time since last prophylactic infusion in hours is to be derived as:
  - $Time(h) = Date/Time\ of\ Bleed\ Start\ Date/Time\ of\ Infusion$  where the start date/time of infusion refers to the last prophylactic infusion received (other than to treat a bleed) prior to the start of the bleed. Time since last prophylactic dose is to be categorized as:
    - $\circ$  <24 hours.

```
24 - <48 hours.

48 - <72 hours.

72 - <96 hours.

>96 hours.
```

• Time since previous bleed are only to be determine if a subject had multiple bleeds and is to be derived as:

```
Time(months)
= (Date/Time \ of \ Current \ Bleed
- Date/Time \ of \ Previous \ Bleed)/365.2425 \times 12
```

- A bleed is considered to be treated with BAX 855 if at least one infusion linked to the particular bleed is present in the *Study Infusion* eCRF panels. Infusions to "Maintain Hemostasis" are not to be summarized as part of treatment for bleeding episodes.
- The number of bleeds per subject overall and by location (target joint, non-target joint, joint and non-joint), causality (spontaneous/unknown and injury), severity (mild, moderate and severe) and timing (weekends, weekdays, morning, evening and afternoon) are to be determined as the count of unique bleeds in each category a subject had during the observation period.
- Annualized bleeding rate (ABR) is to be derived for each treatment regimen the subject had during the study as:

$$ABR = \frac{Number\ of\ unique\ bleeds}{OPE\ (years)\ for\ treatment\ regimen}$$

The ABR is to be analyzed using a generalized linear model fitting a negative binomial distribution with logarithmic link function. Only subjects that have 100 or more EDs are to be included in the models, where total EDs are derived as in Section 6.7: Extent of Exposure.

The model is to be analyzed separately for each of the every 5 days and every 7 days treatment regimen. Baseline age and ABR as continuous covariate and the logarithm of the OPE in years, specific to each treatment regimen, as an offset, is to be included in the model. The following SAS® code is to be used to perform the analysis:

```
PROC GENMOD DATA = <ds>;
   MODEL <bleds> = <baseline_age> <baseline_ABR> / DIST = NEGBIN
   OFFSET = <log_OPE> LINK = LOG;
   LSMEANS <regimen> / BYLEVEL OM CL;
   ODS OUTPUT LSMEANS = <outds>;
RUN;
QUIT;
```

where <ds> refers to the input dataset, <regimen> the particular treatment regimen time of bleed, <ble> the number of bleeds during the observation period, 
 baseline\_age> the age at baseline, 
 baseline\_ABR> the ABR at baseline and <log\_OPE> the logarithm of the OPE in years, specific to the treatment regimen. Point estimates and confidence intervals obtained from the generalized linear model are to be anti-logged prior to presentation.

The twice weekly regimen and PK-tailored regimen will be analyzed together (not separately as per above model) using a generalized estimating equation (GEE) model using the following SAS® code:

```
PROC GENMOD DATA = <ds>;
   CLASS <subject> <regimen>;
   MODEL <bleeds> = <regimen> <baseline_age> / DIST = NEGBIN
   OFFSET = <log_OPE> LINK = LOG;
   REPEATED SUBJECT = <subject> / CORR = EXCH;
   LSMEANS <regimen> / BYLEVEL OM CL;
   ODS OUTPUT LSMEANS = <outds>;
RUN;
```

where <ds>, <regimen>, <bleeds>, <baseline\_age> and <log\_OPE> is define the same as before and <subject> is the subject number.

For both models above, should the model not converge a poisson model will be fitted instead. Should the non-convergence be due to all bleeds equal to zero, the estimate will be presented as zero with no confidence interval.

The model results are to be presented on the FAS and PPAS for:

- The total ABR.
- Annualized joint bleeding rate.
- Annualized non-joint bleeding rate.
- Annualized target joint bleeding rate.
- Annualized non-target joint bleeding rate.
- Annualized injury related bleeding rate.
- Annualized spontaneous/unknown bleeding rate.
- Annualized severe bleeding rate.
- Annualized moderate bleeding rate.
- Annualized minor bleeding rate.
- Annualized weekday bleeding rate.

- Annualized weekend bleeding rate.
- Annualized morning bleeding rate.
- Annualized afternoon bleeding rate.
- Annualized night bleeding rate.
- Annualized bleeding rate at unknown time.

A figure presenting results from the generalized linear model on the total ABR is to be presented for the FAS. Figures are also to be presented showing the number of bleeds within a specific time category since previous prophylactic infusion as well as bleeds overlaid with all treatments received during the study and binding antibodies on the FAS.

ABR for the above categories is to be presented descriptively for the FAS and PPAS. Descriptive statistics on the average duration between bleeding episodes for subjects with more than one bleeding episode and characteristics of bleeding episodes (including number of infusions to treat each bleed, total dose [IU] to treat each bleed, average dose per infusion to treat each bleed [IU/kg], efficacy rating, time since previous prophylactic dose [h] and severity of each bleed) are to be presented for the FAS and PPAS as well. Summaries for bleeding episodes are to be presented by age category, presence of target joints at screening and treatment regimen at time of bleed. Descriptive summaries on the number of infusions to treat a bleed are to include the 95% confidence interval on the median number of bleeds. The 95% confidence interval on the median will be determined using the distribution-free confidence interval for the 50th percentile from the SAS® UNIVARIATE procedure.

Information on bleeding episodes including the course of target joints and ultrasound information is to be listed for the SAS.

#### 7.2 Weight-adjusted Consumption of BAX 855

Weight-adjusted consumption of BAX 855 is discussed in Section 6.7 Extent of Exposure.

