10.4 Medications and Non-Drug Therapies

The following medications are **not** permitted within 30 days before study entry and during the course of the study:

- Any PEGylated medication (eg, PEG-interferon)
- Any investigational drug, biologic, or device, except BAX 855 in case of transitioning subjects

A subject who has taken any of these medications will be considered a protocol deviation.

The use of any FVIII concentrate other than BAX 855 during the course of the study following the first BAX 855 infusion^{xii} will result in the immediate withdrawal of the subject. Every effort should be made to have the Completion/Termination Visit performed. The use of (commercial) ADVATE may be permitted for a short period of time for administrative reasons.

The following medications and non-drug therapies are permitted before study entry and during the course of the study:

- Medications:
 - Hemostatic agents, such as tranexamic acid, are permitted, as indicated by the subject's treating physician, to treat mucosal bleeding during the study
 - Any medications deemed necessary by the subject's physician to treat or prevent any medical condition
 - Any over-the-counter medication used by the subject to treat symptoms or signs
 - Supplemental vitamins, minerals
- Non-drug therapies:
 - Any non-drug therapy (eg, physiotherapy) deemed necessary by the subject's physician to treat or prevent any medical condition

^{xii} This infusion may be the first prophylactic infusion or infusion for the determination of IR for FVIII activity.

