11. ASSESSMENT OF EFFICACY

11.1 Annualized Bleed Rate (ABR)

The primary measure of efficacy is the ABR. The ABR will be assessed based upon each individual bleeding episode, spontaneous or traumatic, recorded in the subject's diary, and/or recorded in the physician/nurse/clinic notes. A bleeding episode is defined as subjective (eg, pain consistent with a joint bleed) or objective evidence of bleeding which may or may not require treatment with FVIII. Bleeding episodes occurring at the same anatomical location (eg, right knee) with the same etiology (eg, spontaneous vs. injury) within 24 hours (± 2 hours) of onset of the first episode will be considered a single bleeding episode. Bleeding occurring at multiple locations related to the same injury (eg, knee and ankle bleeds following a fall) will be counted as a single bleeding episode.

11.2 Overall Hemostatic Efficacy Rating of BAX 855 for the Treatment of Bleeding Episodes

The subject or their caregiver will rate the severity (minor, moderate, or major) of the bleeding episode and will rate the overall treatment response at 24 (± 2) hours after the initiation of treatment using a 4-point efficacy rating scale (Table 4). Efficacy will not be assessed if any other FVIII concentrate is administered for the treatment of bleeding episodes. Since the efficacy rating is based to a large degree on cessation of pain, the investigator/subject shall, in particular in case of injury-related bleeding into one or more than one location, consider the injury-related symptoms when performing the efficacy rating 24 hours after initiating treatment and at resolution of bleed.

As per Table 4, multiple infusions of BAX 855 may be administered for the treatment of a bleeding episode. The overall response to all infusions combined is the rating that will be recorded.

Table 4 Efficacy Rating Scale for Treatment of Bleeding Episodes at 24 ± 2 Hours from the Initiation of Treatment and at Resolution of Bleed	
Excellent	Full relief of pain and cessation of objective signs of bleeding (eg, swelling, tenderness, and decreased range of motion in the case of musculoskeletal hemorrhage) after a single infusion. No additional infusion is required for the control of bleeding. Administration of further infusions to maintain hemostasis would not affect this scoring.
Good	Definite pain relief and/or improvement in signs of bleeding after a single infusion. Possibly requires more than 1 infusion for complete resolution.

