#### 2. STUDY DESIGN

This is a phase 3b, prospective, open label, multi-center study to evaluate the safety and efficacy of BAX 855 for prophylactic use and the control of bleeding episodes in approximately 200 pediatric and adult PTPs  $\leq$  75 years of age with severe hemophilia A. In the Russian Federation, safety and efficacy are only to be assessed in adults aged  $\geq$  18 and < 75 years at the time of enrollment. The study plans to include subjects from other BAX 855 studies and BAX 855-naïve subjects.

Subjects are to receive either a fixed dose prophylaxis with BAX 855 consisting of  $45 \pm 5$  IU/kg for subjects aged  $\geq 12$  years or  $50 \pm 10$  IU/kg for subjects aged  $\leq 12$  years (in all countries except the Russian Federation) twice weekly or, subjects can decide to receive a pharmacokinetic (PK)-tailored prophylactic BAX 855 dosing regimen based on the subject's individual PK to maintain FVIII trough levels of  $\geq 3\%$ . Other treatment regimens were allowed prior to protocol amendment four.

Subjects are to be treated on the specified prophylactic treatment regimen until they reach at least 100 exposure days (EDs) (as accumulated across all BAX 855 studies).

It is to be noted that the use of any FVIII concentrate other than BAX 855 during the course of the study following the first BAX 855 infusion is not permitted. The use of (commercial) ADVATE may be permitted for a short period of time for administrative reasons. It is also to be noted that ADVATE was allowed as rescue medication in

previous versions (prior to amenmdent four) of the protocol for this study under which a number of subjects have been enrolled.

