#### 4.4 Per Protocol Analysis Set (PPAS)

The per protocol (PPAS) analysis set is to comprise all subjects in the FAS who had no major deviations from the protocol affecting the study results. Protocol deviations are to be obtained from the Clinical Trial Management System (CTMS).

Prior to performing any analysis as set out in this SAP, a meeting is to be held discussing the impact of any major protocol deviation on the analysis. At this meeting, the decision is to be made on whether a subject is to be excluded from the PPAS analysis set or not. The meeting is to be attended by participants from at least Biostatistics and Medical.

Below is a list of possible major deviations that may influence the study results that will be discussed at the analysis set assignment meeting:

- Subject less than 75% exposed to BAX 855 as derived in Section 6.8: Measurements of Treatment Compliance.
- Subject less than 75% compliant to planned dosing regimen.
- More than 10% of treated bleeds have no efficacy rating.
- Use of expired IP.
- Subject did not reach 100 EDs across all BAX 855 studies.
- Use of any FVIII product other than ADVATE, as determined by the medical team.

It should be noted that the above will not necessarily lead to immediate exclusion from the PPAS, but will be discussed prior to locking the database. The database is not allowed to be locked until final approval on the PPAS has been obtained.

During the course of the study, data review meetings are to be held on a regular basis. During these meetings the quality of the data including any potential protocol deviations are to be identified. All protocol deviations identified at these meetings are to be included into the CTMS upon team agreement.

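### SAP 7.1 classes a bleed as treated with BAX 855 on one linked infusion and has no step for bleeds also given another FVIII concentrate, so it does not carry out Protocol 11.2

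*SAP*

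**What the plan says.** **Protocol.** Section 11.2, on the haemostatic efficacy rating, states: "Efficacy will not be assessed if any other FVIII concentrate is administered for the treatment of bleeding episodes". Section 10.5.1 lists the rating among the items recorded for each bleeding episode and makes no exception for other FVIII. Section 10.4 calls for withdrawal when another FVIII concentrate is used, but adds: "The use of (commercial) ADVATE may be permitted for a short period of time for administrative reasons".

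**SAP.** Section 7.1 gives the working definition: "A bleed is considered to be treated with BAX 855 if at least one infusion linked to the particular bleed is present", with the Study Infusion panels as the source. Infusions given to maintain haemostasis "are not to be summarized as part of treatment for bleeding episodes"; no other restriction is attached. The same section plans descriptive summaries on the FAS and PPAS that include "number of infusions to treat each bleed, total dose [IU] to treat each bleed" and the efficacy rating, with no filter for other FVIII products. Section 2 notes that "ADVATE was allowed as rescue medication in" protocol versions before amendment 4, and that a number of subjects were enrolled under them. Section 4.4 lists possible major deviations to be discussed for the PPAS. The item on other products reads: "Use of any FVIII product other than ADVATE, as determined by the medical team". Section 5.7 lists two changes from the protocol's analyses, on imputation and on the ABR model.

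**The concern.** The efficacy rating and the number of infusions per bleed are secondary outcomes, and Protocol 13.4.2.1 adds dose per bleed to the description of how well BAX 855 treats bleeds. Protocol 11.2 takes bleeds given another FVIII concentrate out of the efficacy assessment, since the response cannot then be attributed to BAX 855 alone. The SAP governs the programming, and a programmer following it has no instruction to identify or remove those bleeds. At stake is whether the treated-bleed results describe BAX 855 or, for some bleeds, BAX 855 plus another product, and whether infusion counts and doses are complete.

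**Working it through.** The plan states no figure to reproduce. The check compares the texts and then bounds the effect.

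**1. Can a bleed receive both products?** Yes, by two routes: rescue ADVATE before amendment 4 (SAP 2), and short-term commercial ADVATE under the current text (Protocol 10.4). Withdrawal after use of another product does not remove the subject's earlier bleeds from the FAS, which contains everyone with at least one BAX 855 infusion.

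**2. Does any other provision restore the exclusion?**

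| Provision | Effect on a co-treated bleed |
|---|---|
| SAP 7.1 carve-out | Covers maintenance infusions only |
| SAP 4.4, item on other FVIII | Subject level, open to discussion, does not name ADVATE, no effect on the FAS |
| SAP 4.4, item on more than 10% of treated bleeds unrated | Works the other way: a bleed correctly left unrated under Protocol 11.2 counts against the subject |
| SAP 6.6 | Concomitant medications are listed, not summarised or linked to bleeds |
| SAP 5.7 | No departure from Protocol 11.2 declared |

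None of these restores it.

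**3. What enters the summaries?**
- *Rating.* Protocol 10.5.1 asks for one for each bleed, so a co-treated bleed may have one. If it was left blank, SAP 5.8 would probably show it as a not-reported category with a percentage.
- *Infusions and dose.* SAP 4.2 names the Study Infusion panels as a source for BAX 855 dosing. If they hold only BAX 855, a bleed given 1 BAX 855 and 2 ADVATE infusions is recorded as 1 infusion instead of 1 + 2 = 3. At equal doses, 2/3 of the FVIII given is missing. If the panels also hold ADVATE, the rule's unqualified reference to an infusion could class an ADVATE-only bleed as treated with BAX 855.

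**4. Size of the effect on the rating.** Let s be the share of analysed bleeds also given another FVIII, p_mix the proportion of those rated excellent or good, and p_only the proportion among BAX 855-only bleeds.

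Reported rate = (1 − s) × p_only + s × p_mix

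Shift relative to exclusion = s × (p_mix − p_only)

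The absolute shift is therefore at most s. The documents give none of the three quantities, so the values below are assumptions.

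| s | Largest possible shift | Shift if the rates differ by 20 points |
|---|---|---|
| 1% | ±1 point | ±0.2 point |
| 5% | ±5 points | ±1.0 point |
| 10% | ±10 points | ±2.0 points |

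**5. Sign.** Take s = 10% and p_only = 90%.
- With p_mix = 50%: 0.90 × 90% + 0.10 × 50% = 81% + 5% = 86%. Retention lowers the rate by 4 points.
- With p_mix = 100%: 81% + 10% = 91%. Retention raises it by 1 point.

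**The case against.** The strongest reply is that the two texts do not contradict each other. Protocol 11.2 governs whether efficacy is assessed; if sites followed it, there is no rating to summarise. SAP 7.1 only defines a label, and its list of summaries does not name that label as a filter. This stands in part: retention follows from the lack of an exclusion, not from a stated rule to keep these bleeds. It does not settle the matter, because Protocol 10.5.1 asks for a rating for each bleed and infusion counts and doses would enter in any case.

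A second reply is that Protocol 11.2 concerns the rating only. Infusion number and consumption have their own sections (11.3 and 11.5) without such an exclusion. This stands. Removing co-treated bleeds from those summaries is justified by incomplete counts, not by 11.2.

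A third reply is that few bleeds may be affected. The current protocol calls for withdrawal on use of another FVIII, its ADVATE exception is for administrative reasons, and a bleed given only rescue ADVATE has no linked BAX 855 infusion if the panels hold only BAX 855. This also stands: the number is unknown and may be small. On the PPAS, Section 4.4 lists possible deviations only, so the meeting could still consider ADVATE use.

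A reader might infer that retention inflates the BAX 855 success rate, because rescue follows a poor first response and the final rating credits the rescue product. The documents do not support that direction. Table 4 ties the two best ratings to the response after a single infusion, so a poor first response fits the lower ratings, and keeping such bleeds could lower the success rate. Inflation of 5 points at s = 10% would need p_mix − p_only = 50 points, hence a BAX 855-only success rate of 50% or less. Nothing in the documents indicates that.

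**Conclusion.** The point holds as a gap between the protocol and the SAP. The SAP does not implement the Protocol 11.2 exclusion and does not declare a departure. Recorded ratings of co-treated bleeds enter the BAX 855 summary on the FAS, and on the PPAS unless the subject is removed at the analysis-set meeting. If the infusion panels hold only BAX 855, infusion count and dose are understated for each such bleed by what the other product contributed. The effect on the rating is bounded by the share of co-treated bleeds, which is not given, and may go either way. The finding concerns descriptive secondary results; the spontaneous ABR counts bleeds whatever their treatment and is unaffected.

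**What to change.** In SAP 7.1, add a bleed-level flag for any bleed for which another FVIII concentrate, including ADVATE, was given as treatment of that bleed, derived from the infusion and concomitant-medication data. Then:

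- exclude flagged bleeds from the efficacy-rating summary, as Protocol 11.2 requires;
- exclude them from the infusions-per-bleed and dose-per-bleed summaries, stating that this is an extension for consistency because a BAX 855-only count is incomplete there; for the average dose per bleed in SAP 6.7, remove them from both numerator and denominator;
- keep them in all ABR analyses;
- report their number on a separate line;
- leave them out of the SAP 4.4 criterion on treated bleeds without a rating.

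If the sponsor means to keep these bleeds in the rating summary, SAP 5.7 should list that as a change from the protocol and give the reason.

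The cost is a few lines of SAP text and one derived flag, with no new data collection. Linking concomitant FVIII to a particular bleed may need medical review where the reason for use is unclear. The denominators become slightly smaller, and the results may move in either direction.
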